## 5.4. Statistical analysis plan

### 5.4.1. Analysis of complete remission

The probability of complete remission (CR, Appendix II) will be estimated by the number of CR divided by the total number of patients evaluable for response. A 95% one-sided exact binomial confidence interval of the form  $(\pi_{\text{L}}, 1)$  for the true probability of CR will be calculated.

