### **5.2. Sample Size/Accrual rate**

#### **5.2.1 Sample size**

This study is expected to require a minimum of 16 patients (at the interim evaluation of response) and a maximum of 44 response-evaluable patients unless undue toxicity is encountered. We anticipate accruing up to 9 additional patients (~20%) to account for patients who may prove unevaluable (i.e. ineligibility, cancellations, death or major violations). Therefore, our overall sample size will be a maximum of 53 patients.

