### **5.3. Study design**

**5.3.1 Definition of complete remission (CR):** An evaluable patient will be classified as having complete remission if they meet the criteria in Appendix II.

**Decision Rule (Simon two-stage design):** The largest CR rate where the proposed treatment regimen would be considered ineffective in this population is 35%. Subsequent studies will be warranted if the CR rate is 50% or higher or the CR rates are similar to historical data but

the disease-free survival and the overall survival are improved in comparison to our institution's historical cohort. The following optimal Simon two stage design uses 44 patients to test the null hypothesis that the true CR rate in the given patient population is at most 35%.

**Stage 1:** Enter 16 evaluable patients. If 5 or fewer patients have a CR in this timeframe, we will consider this early evidence that this treatment regimen is not sufficiently efficacious in this patient population, and the accrual of patients will be stopped. If 6 or more patients have a CR, then accrual will continue in the second stage of this trial.

**Stage 2:** Enter an additional 28 evaluable patients to the trial. If 19 or more patients achievea complete remission, the treatment will be promoted for further consideration. This design has  $\alpha=0.15$  and  $\beta=0.20$ ; the large value of  $\alpha$  is appropriate in an early phase trial. If the probability of CR is 35%, the expected sample size is 30.3 patients, i.e., the probability that the trial will be halted after 16 patients is 48.9%.

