### **5.3.2 Monitoring for treatment-induced mortality**

The trial will be continually monitored to ensure that treatment-induced mortality is not excessive, defined as  $>0.20$  of patients treated. A safety-evaluable patient is a patient

who was consented and started the protocol chemotherapy. All safety-evaluable patients, not just those evaluable for clinical response, are counted in the interim analysis for mortality. The cutpoints are listed in Table 2.

**Table 2.** Stopping rule for excessive mortality. The trial will be halted if, for the number of patients in the following table, the number of deaths is greater than or equal to the given number.

# Patients	# Deaths	# Patients	# Deaths
4	3	24	7
6	3	26	8
8	3	28	8
10	4	30	8
12	4	32	9
14	5	34	9
16	5	36	10
18	6	38	10
20	6	40	11
22	7	42	11

Justification of the stopping rule: It was assumed that under standard of care, the probability of death is  $\pi=0.2$ . A beta-binomial model is assumed with  $\alpha=2$  and  $\beta=8$ . If the number of deaths,  $x$ , is greater than the value in the Stopping Rule table for the number of patients,  $n$ , then:

$$P(\pi>0.2|\alpha,\beta,x,n)>0.75.$$

Under different assumptions of the true probability of death (True P(Death)), the expected number of patients ( $E(n)$ ) and the probability of the trial stopping early ( $P(Stop Early)$ ) were determined by Monte Carlo simulation:

True P(Death)	E(n)	P(Stop Early)
0.20	28.3	0.513
0.25	22.9	0.720
0.30	15.8	0.900
0.35	11.5	0.973
0.40	8.4	0.994
0.45	6.9	0.996

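### Does the one-sided 95% bound for the CR rate in section 5.4.1 conflict with a go rule built at alpha 0.15?

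*Combined protocol and SAP*

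**What the plan says.** Section 5.3 (Decision Rule) sets the null value: "The largest CR rate where the proposed treatment regimen would be considered ineffective in this population is 35" per cent. It then says that the design uses 44 patients "to test the null hypothesis that the true CR rate in the given patient population is at most 35" per cent. Stage 1 enters 16 evaluable patients and stops at 5 or fewer CRs. Stage 2 adds 28, and with 19 or more CRs in total "the treatment will be promoted for further consideration". The same paragraph gives alpha 0.15, beta 0.20, an expected sample size of 30.3 and a 48.9% chance of stopping at stage 1 when the CR rate is 35%. It defends the large alpha on the ground that it "is appropriate in an early phase trial".

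Section 5.4.1 is the planned analysis of CR. The CR probability "will be estimated by the number of CR divided by the total number of patients evaluable for response". Beside it the plan puts "A 95% one-sided exact binomial confidence interval of the form" (π_L, 1). It names no p-value and does not mention the stages. Section 5.4.2 covers survival and predictors only.

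**The concern.** The two sections work at different error levels. The test allows a false promotion rate of up to 15%; the interval allows 5%. The interval also treats the final count as one binomial sample, although the trial can stop after 16 patients.

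A trial could therefore end with the regimen promoted while the only interval planned for its primary endpoint still includes the rate that the protocol calls ineffective. A reader who judged the regimen by whether the bound clears 35% would be using a much stricter rule than the one the trial was sized for, and the investigators would have to explain the difference after seeing the result. A p-value against 35%, or a bound at the design's own level that respects the stages, might seem to be missing.

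**Working it through.** **Inputs, all from section 5.3 except the last.** n1 = 16, stop at 5 or fewer; n = 44 (28 more), promote at 19 or more; null 0.35; target 0.50; alpha 0.15; beta 0.20. Section 5.4.1: one-sided 95% exact bound.

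**1. Reproduce the design.** Let X1 ~ Bin(16, p), X2 ~ Bin(28, p) and S = X1 + X2.

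- P(stop at stage 1 | 0.35) = P(X1 ≤ 5) = 0.48996. The plan prints 48.9%, apparently truncated.
- Expected sample size = 16 + 28 × (1 − 0.48996) = 30.28. The plan says 30.3.
- P(promote | p) = Σ over x1 = 6 to 16 of P(X1 = x1) · P(X2 ≥ 19 − x1). This is 0.142 at p = 0.35 and 0.801 at p = 0.50.

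The design is as stated, with attained level 0.142 against a ceiling of 0.15. A search over two-stage designs returns the same 5/16 and 18/44 as Simon-optimal.

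**2. Bounds and p-values at 44 patients.** The single-stage bound at level 1 − a is the Clopper-Pearson limit, the a-quantile of Beta(s, 45 − s). The two-stage bound solves P(X1 ≥ 6 and S ≥ s | p) = a. The two-stage p-value is that probability at p = 0.35.

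| CRs | Go? | Planned 95% | Two-stage 95% | Single-stage 85% | Two-stage 85% | Single-stage p | Two-stage p |
|---|---|---|---|---|---|---|---|
| 18 | no | 0.284 | 0.291 | 0.325 | 0.334 | 0.251 | 0.207 |
| 19 | yes | 0.304 | 0.309 | 0.346 | 0.353 | 0.163 | 0.142 |
| 20 | yes | 0.325 | 0.329 | 0.368 | 0.372 | 0.099 | 0.090 |
| 21 | yes | 0.346 | 0.349 | 0.390 | 0.393 | 0.056 | 0.052 |
| 22 | yes | 0.368 | 0.369 | 0.412 | 0.414 | 0.029 | 0.028 |

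The planned bound includes 35% at exactly three promoting counts: 19, 20 and 21. The confidence level causes this, not the neglect of the stages, because a two-stage 95% bound includes 35% at the same three counts. Only the two-stage 85% bound agrees with the go rule throughout.

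**3. How often.** Share of promotions at 19–21 = 1 − P(X1 ≥ 6 and S ≥ 22) / P(promote):

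- p = 0.35: 1 − 0.028/0.142, about 81%
- p = 0.40: 68%
- p = 0.45: 51%
- p = 0.50: 1 − 0.545/0.801 = 32%
- p = 0.55: 16%

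**4. Is the planned bound valid?** Over true CR rates from 0.30 to 0.60 in steps of 0.0005, with the stage 1 stop included, its lowest coverage is 0.950. Ignoring the stages does not cost it its nominal level. The raw proportion is biased downward by 0.031 at 0.35 and 0.015 at 0.50, which is small and in the cautious direction.

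**5. What would a matched bound add?** The cut-off of 19 is the smallest total whose two-stage tail probability at 35% is 0.15 or less (0.142 at 19, 0.207 at 18). The two-stage 85% bound inverts the same probability, so it must clear 35% at 19 and above and fail below. It repeats the count rule on another scale.

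It also has drawbacks. At 19/44 the report would show 0.304 and 0.353, on opposite sides of 35%. It ranks every outcome that reaches 44 patients above every stop at 16, so at 6 to 10 CRs of 44 its lower limit exceeds the raw proportion: at 6/44, 0.234 against 6/44 = 0.136. Those outcomes are rare (probability 0.003 at a true rate of 0.35, 0.02 at 0.20), but the pre-specified text would have to cover them.

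**The case for a change.** The best case for a change is that the bound in section 5.4.1 is the only interval planned for the primary endpoint, that it is not labelled as descriptive, and that a one-sided lower limit invites comparison with the null. Used as a test, it would reject with probability 0.028 at a 35% CR rate and 0.545 at 50%, where the design has 0.142 and 0.801. Nor are the affected counts a corner case: they are half of all promotions at a true rate of 45%. Two or three sentences written in advance would settle how to read them, at no cost in patients or data.

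The figures stand, and so does the possibility of misreading. But those rejection probabilities belong to a rule that the plan never states. Section 5.4.1 only has the interval calculated; promotion in section 5.3 depends on the count alone. The alpha 0.15 inference is not missing either: in a Simon design, reaching 19 of 44 is the test result, and section 5.3 gives its null, error rates and the reason for the large alpha. An estimation interval need not share the test's error level. A 95% bound of 0.304 beside a promotion at 19/44 tells the reader, correctly, that the evidence is thin.

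One narrower point survives. If someone adds a p-value for a trial that completes the design, the single-stage value at 19/44 is 0.163, above 0.15, while the value that respects the stages is 0.142. Analysts who know the design was two-stage would use the latter, and the plan does not ask for either.

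**Conclusion.** No change follows. The bound and the go rule differ at three counts, 19 to 21 of 44, which hold 32% of promotions at the 50% target and 68% at a true CR rate of 40%. At those counts the decision, the type I error (0.142), the power (0.801) and the coverage of the 95% bound (at least 0.950 for true rates from 0.30 to 0.60) are all sound under the plan as written. The difference reflects a liberal screening rule reported with a conventional precision bound, a fair choice in a single-arm phase II trial. The report need only say that promotion rests on the count rule of section 5.3 and that the 95% bound describes precision, which an analyst can do without an amendment.

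The figures for 44 patients assume that the trial runs to one of its two designed sizes, 16 or 44 evaluable patients. Under section 5.2.1 the target is "a maximum of 44 response-evaluable patients unless undue toxicity is encountered", and a mortality halt under section 5.3.2 could end the trial at another size. The planned exact bound can still be computed there, whereas a bound tied to the 16/44 design would need a fallback.

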### 5.4.2 Analysis of secondary endpoints

Overall and progression-free survival functions will be estimated by the product limit (Kaplan-Meier) method. The median survival and its 90% confidence interval will also be reported.

Proportional hazards (Cox) regression will be used to describe the relationship between age, cytogenetic status (poor, intermediate, favorable), percent of blast in the bone marrow prior to therapy and percent expression of CD33 in the leukemia blasts to overall and progression-free survival. Likelihood ratio tests will be used to identify statistically significant ratios and profile likelihood confidence intervals will be estimated for hazard ratios of statistically significant predictors. Logistic regression will be applied in a similar fashion to determine predictors of complete remission.

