## **1.0 INTRODUCTION**

### **1.1 Study objectives**

Primary Objective: To evaluate the response rate and toxicity of the combination of mitoxantrone, etoposide and gemtuzumab ozogamicin as second line therapy in patients with acute myeloid leukemia (AML) who have failed the first induction therapy.

Secondary Objectives: To assess the progression-free survival, overall survival and treatment related mortality in patients with AML treated with the combination of mitoxantrone, etoposide and gemtuzumab ozogamicin.

To explore if age, cytogenetic status, percent of blast in the bone marrow prior to therapy or percent expression of CD33 in the leukemia blasts are predictive of complete remission, overall survival or progression-free survival in patients with AML treated with the combination of mitoxantrone, etoposide and gemtuzumab ozogamicin.

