## **5.0 STATISTICAL CONSIDERATIONS AND METHODOLOGY**

### **5.1 Number and evaluable of patients**

This is a phase II study of the combination therapy of GO, mitoxantrone and etoposide as second line therapy in patients with acute myeloid leukemia. The study is designed to assess the therapeutic efficacy and the toxicity profile using Simon's optimal two-stage phase II design to permit early stopping of the trial if there is strong evidence that the studied treatment is ineffectual.

To be evaluable for clinical response, a patient must:

1. Receive a total of 5 days of mitoxantrone and etoposide,
2. Receive 1 dose of GO and
3. Have a follow-up bone marrow biopsy to evaluate the response to therapy.

Additional participants will be recruited to replace those who are not evaluable for clinical response. The accrual target is a maximum of 44 response-evaluable patients. All participants who begin treatment will be counted in the interim analysis for excess mortality.

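### Section 5.4.2 plans confidence intervals only for predictors that reach significance, so non-significant results, the likelier outcome for modest effects at this sample size, carry no measure of what they exclude

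*Combined protocol and SAP*

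**What the plan says.** Section 1.1 places the predictor question among the secondary objectives and words it as exploration: "To explore if age, cytogenetic status, percent of blast in the bone marrow prior to therapy" or CD33 expression predicts CR, OS or PFS.

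Section 5.4.2 names the predictors as "age, cytogenetic status (poor, intermediate, favorable), percent of blast in the bone marrow prior to therapy and percent expression of CD33" in the leukemic blasts, and presents Cox regression as a way to describe how they relate to OS and PFS. The reporting rule follows in one sentence. First, "Likelihood ratio tests will be used to identify statistically significant ratios"; then, "profile likelihood confidence intervals will be estimated for hazard ratios of statistically significant predictors". For CR, "Logistic regression will be applied in a similar fashion to determine predictors of complete remission", so the same rule passes to odds ratios.

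The plan's other intervals do not depend on a test. Section 5.4.1 gives a one-sided 95% exact interval for the CR probability, and Section 5.4.2 gives a 90% interval for median survival. For the predictor analysis the documents state no significance level, no interval level, no handling of multiplicity, and not whether predictors enter jointly or one at a time.

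On numbers, Section 5.1 says "The accrual target is a maximum of 44 response-evaluable patients" and Section 5.2.1 says "our overall sample size will be a maximum of 53 patients". Section 5.4.2 does not say which of these groups supplies the OS and PFS models.

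**The concern.** An exploratory analysis in a small single-arm trial is useful mainly for its estimates and their precision. The rule ties precision to the p-value. A predictor that misses significance gets a test result and no planned interval, so a reader cannot tell a predictor shown to matter little from one that the data could not assess. CD33 expression is the clearest case. It is the target of gemtuzumab ozogamicin and an entry criterion (Section 2.1), and its effect could well be too modest to reach significance here.

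The rule also acts on the other side. In a small sample an estimate must be fairly large to be significant, so those that pass are too large on average. If they alone carry intervals, they stand out in the report.

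**Working it through.** **The plan's own figures.** The documents give no figure for the predictor analysis. The Simon design fixes the patients available to it, so it was checked first. With p0 = 0.35, stage 1 stops on 5 or fewer CRs in 16, and promotion needs 19 or more in 44:
- P(stop at stage 1) = P(X ≤ 5 | 16, 0.35) = 0.490 (stated 48.9%).
- E(N) = 16 + (1 − 0.490) × 28 = 30.28 (stated 30.3).
- Type I error 0.142 (limit 0.15); power at 50% CR 0.801.

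The design reproduces. The analysis may therefore have 44 response-evaluable patients, or 16 if the trial stops early ("If 5 or fewer patients have a CR in this timeframe").

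**What a null survival result would exclude.** For a continuous predictor per SD, SE(log HR) ≈ 1/√d for d events. At an estimated HR of 1.00 the 95% interval is exp(±1.96/√d). The upper limit is also the smallest HR above 1 that would pass a two-sided 5% test. The chance of passing at a true HR of 1.3 is about Φ(ln 1.3 × √d − 1.96), with ln 1.3 = 0.262. Event counts and the 5% level are assumptions.

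| Events d | SE | 95% interval at HR 1.00 | Chance of significance, true HR 1.3 |
|---|---|---|---|
| 53 | 0.137 | 0.76 to 1.31 | 48% |
| 44 | 0.151 | 0.74 to 1.34 | 41% |
| 35 | 0.169 | 0.72 to 1.39 | 34% |
| 25 | 0.200 | 0.68 to 1.48 | 26% |
| 16 | 0.250 | 0.61 to 1.63 | 18% |

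Even if all 53 enrolled patients had an event, a true HR of 1.3 per SD would miss significance more often than not. A stronger effect behaves differently: at HR 1.5 the chance is 67% with 35 events and 77% with 44.

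**What a null CR result would exclude.** For one covariate per SD, SE(log OR) ≈ 1/√(n p(1−p)). With n = 44 and an assumed CR rate of 45%, 44 × 0.45 × 0.55 = 10.89, SE = 0.303, and exp(±1.96 × 0.303) = 0.55 to 1.81. At the design's null rate of 35%, 44 × 0.35 × 0.65 = 10.01 and the interval is 0.54 to 1.86. At the target of 50% it is again 0.55 to 1.81.

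**How far selected estimates run high.** Among significant results the mean log HR is about θ + SE × φ(z)/Φ(−z), where θ is the true log HR and z = 1.96 − θ/SE; the opposite tail is negligible here. With d = 35 and θ = 0.262, θ/SE = 1.552 and z = 0.408. The mean is 0.262 + 0.169 × (0.367/0.342) = 0.444, an HR of 1.56, or 1.7 times the true log HR. For a true HR of 1.5 with 35 events the result is 1.64, or 1.2 times.

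Simulated Cox fits (n = 44, about 80% events, likelihood ratio test at 5%) agree in direction:
- True HR 1.3: geometric mean 1.62 among significant fits, 1.32 over all fits.
- True HR 1.5: 1.72 among significant fits, 1.52 over all fits.

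The all-fits means are close to the truth, so the excess comes from selection.

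**The case against.** The best defence is that the analysis is exploratory, feeds no decision, and that the sentence never uses the word only. That is fair as to weight. The Simon rule, the mortality rule and the CR estimate with its interval do not depend on it. But no other section plans intervals for the remaining predictors, so the plan as written does not provide them, and an aim of exploring and describing argues for showing them all.

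Several stronger readings are tempting and do not stand:

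- *Non-significant results will be suppressed.* The plan does not say that point estimates or p-values will be withheld. What is unplanned is the interval.
- *Everything rests on at most 44 patients.* That ceiling is for response-evaluable patients. Up to 53 may be enrolled, and the OS and PFS population is not stated.
- *There is a 46% chance of a false positive, and the rule causes it.* The figure is 1 − 0.95^12, from four predictors on three outcomes. It assumes a 5% level that the documents do not give and 12 independent tests, although the outcomes come from the same patients; with assumed correlations of 0.5 to 0.85 between outcomes it is about 37% to 40%. It is a multiplicity issue and is the same whichever intervals are printed.
- *A true OR of 1.5 will be reported as about 2.6.* That size needs a joint model with five degrees of freedom, which the plan does not specify, and it mixes selection with small-sample logistic bias: in one such simulation the median was already 1.61 over all fits. With a single predictor the medians were 1.52 over all fits and 2.31 among significant ones.
- *The selected intervals are invalid.* The procedure keeps its approximate unconditional coverage. Coverage among significant results alone is lower for weak effects (about 93% at a true HR of 1.3 with 35 events) and is not degraded for stronger ones (about 96% at 1.5).

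It is also true that reporting every interval leaves the significant estimates as they are.

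**Conclusion.** The concern holds as a gap in reporting. Intervals are planned for significant predictors and for no others, so a non-significant result, which is likely for a modest effect, comes with no planned statement of what it excludes. That can be a good deal: HRs per SD of up to about 1.34 to 1.48 (44 to 25 events), and an OR for CR of up to about 1.8. Selected Cox estimates run high on average (about 1.6 for a true 1.3), less so for stronger continuous predictors.

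These sizes rest on a two-sided 5% level, the event counts shown, a CR rate near 45%, one continuous covariate per model and the normal approximation. The documents fix none of these for this analysis. Importance is modest: the analysis is exploratory and the primary CR decision does not depend on it.

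**What to change.** Replace the sentence in Section 5.4.2 on likelihood ratio tests and profile likelihood intervals with:

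*Hazard ratios (OS, PFS) and odds ratios (CR) with 95% profile likelihood confidence intervals will be reported for all four prespecified predictors, whatever the p-value; p-values are exploratory and unadjusted for multiplicity.*

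This also settles the interval level, which is now unstated. If the authors keep any statement about significance, they should give its level.

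The cost is one sentence. The models are already planned, and no patient, visit, assay or change to the design is needed. The change does not correct the upward bias of estimates picked out by a test, nor does it control multiplicity. It ensures that those estimates are no longer the only ones shown with their precision.

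### The logistic models for complete remission use ordinary likelihood on at most 44 patients, with no entry mode, test level or rule for sparse cytogenetic classes; Firth's penalised likelihood would suit better

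*Combined protocol and SAP*

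**What the plan says.** Section 1.1 sets a secondary aim: "To explore if age, cytogenetic status, percent of blast in the bone marrow prior to therapy or percent expression of CD33" predict complete remission (CR), overall survival or progression-free survival.

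Section 5.4.2 covers the survival outcomes with Cox regression, with cytogenetic status in three classes (poor, intermediate, favorable). On testing it says "Likelihood ratio tests will be used to identify statistically significant ratios", and on estimation "profile likelihood confidence intervals will be estimated for hazard ratios of statistically significant predictors". For CR it adds only: "Logistic regression will be applied in a similar fashion to determine predictors of complete remission".

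The sample comes from the two-stage design. Section 5.1 states: "The accrual target is a maximum of 44 response-evaluable patients". Under section 5.3, accrual ends at the first stage under this rule: "Enter 16 evaluable patients. If 5 or fewer patients have a CR in this timeframe". Otherwise: "Enter an additional 28 evaluable patients to the trial".

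Section 5.4.2 names no penalised or exact method, so ordinary maximum likelihood is the natural reading. It is silent on four points:
- joint or single entry of predictors
- the significance level
- what happens when a cytogenetic class contains only responders or only non-responders
- whether the models are fitted after a stage-1 stop

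The documents give no cytogenetic distribution.

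**The concern.** Four predictors, one with three levels, need five slopes if fitted together. At 44 patients the smaller outcome group has about 15 (44 × 0.35 = 15.4) to 22 (44 × 0.50) patients. After a stage-1 stop there are 16 patients and at most 5 responders.

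Two things can go wrong at this size. First, if every patient in a small cytogenetic class has the same outcome, the maximum-likelihood odds ratio for that class is zero or infinite and its profile interval is open on one side. Second, the chi-square reference for the likelihood ratio test is too liberal when there are few responders per coefficient.

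Section 5.4.2 gives intervals only for significant predictors, and a class with uniform outcome is more likely to be among them. At stake is the quality of the predictor results: too many false positives, and odds ratios that cannot be reported as numbers.

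**Working it through.** **Design figures.** Section 5.3 gives 16 then 28 patients, a stop at 5 or fewer CRs, and CR rates of 35% and 50%.
- Stop probability P(X ≤ 5), X ~ Bin(16, p): 0.490 at p = 0.35 (plan: 48.9%) and 6,885/65,536 = 0.105 at p = 0.50.
- Expected size at 35%: 16 + 28 × (1 − 0.490) = 30.3 (plan: 30.3).

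The plan's figures reproduce to rounding. A 16-patient data set is about as likely as not at 35% CR and uncommon at 50%.

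**No finite estimate at 44 patients.** Let f be the favorable share (an assumption) and p the CR rate, with CR unrelated to cytogenetics. The chance that at least one favorable patient is present and all favorable patients share one outcome is

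(1 − f(1 − p))^44 + (1 − fp)^44 − 2(1 − f)^44.

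At p = 0.35:
- f = 5%: 0.2337 + 0.4599 − 0.2093 = 0.484
- f = 10%: 0.0520 + 0.2085 − 0.0194 = 0.241
- f = 20%: 0.0022 + 0.0410 − 0.0001 = 0.043

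At p = 0.50 the first two terms are equal:
- f = 5%: 2 × (0.3282 − 0.1047) = 0.447
- f = 10%: 2 × (0.1047 − 0.0097) = 0.190
- f = 20%: 2 × (0.0097 − 0.0001) = 0.019

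Simulation, which also counts the other classes and the joint model, gives 45-51%, 19-24% and 2-5% at these shares, 7-11% at a 15% share, and about 1% or less with equal thirds. After a stage-1 stop the figure is 49-68% with the cytogenetic factor alone and about 66-73% in the joint model, so about half to three quarters.

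**Test error.** Simulation with CR independent of every predictor: three independent normal covariates plus the three-level factor (favorable share varied, intermediate 50%, rest poor; also equal thirds). There were 4,000 data sets per setting for maximum likelihood and up to 2,000 for Firth, with chi-square critical values at an assumed 5%. The stopped trial is 16 patients with CRs drawn from Bin(16, p) given 5 or fewer.

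| Setting | Ordinary, single entry | Ordinary, joint entry | Firth, joint entry |
|---|---|---|---|
| 44, continuous predictor | 5.0-6.4% | 6.7-7.5% | 4.5-5.0% |
| 44, cytogenetic factor | 5.1-6.7% | 6.6-8.6% | 3.4-4.6% |
| 16 after stop, continuous | 6.8-8.0% | 17.9-22.0% | 2.5-3.4% |
| 16 after stop, cytogenetic | 6.9-8.7% | 18.3-26.2% | 1.2-1.6% |

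The Monte Carlo standard error for maximum likelihood is √(0.07 × 0.93/4,000) ≈ 0.4 points near 7% and √(0.2 × 0.8/4,000) ≈ 0.6 points near 20%. Smaller simulations of 700 data sets per setting put joint-model error at 44 patients at 6-9% for ordinary likelihood and 4-6% for Firth. All Firth estimates were finite.

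**Effect of reporting only significant predictors.** Under single entry at 44 patients and 35% CR, the share of falsely significant cytogenetic results that involve a class with uniform outcome was about 71%, 59% and 35% at favorable shares of 5%, 10% and 20%. After a stage-1 stop, with 10-20% favorable, it was above nine in ten.

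**Multiplicity.** Four independent exact 5% tests give 1 − 0.95^4 = 18.5% for at least one false positive. The joint model at 44 patients gave 23-27% with ordinary likelihood and 16-19% with Firth.

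**The case against.** The strongest reply is that the large figures belong to a model the plan does not specify. Section 1.1 joins the four factors with an or, which suits one predictor at a time. On that reading the error at 44 patients is 5.0-6.7%, and after a stop about 7-9%. This stands: a reader might infer that the plan carries an error of 18% or more after an early stop, but the documents support that only under joint entry.

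A reader might also infer that estimates will often be infinite at 44 patients. That needs a favorable share near 5-10%, and no share is given; at 20% the problem is uncommon.

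The 5% benchmark is an assumption too. The plan uses a design α of 0.15 and a 90% interval for median survival elsewhere, and no level here.

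A uniform class does not defeat the planned method. The likelihood ratio test can still be computed, and the open-ended profile interval is a valid one-sided bound. What is lost is a finite odds ratio.

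Merging cytogenetics into two classes would remove nearly all separation at 44 patients under ordinary likelihood: 0.05-0.25% of trials with an assumed 40% poor-risk share. But it gives up a classification that the plan chose. Finally, the aim is exploratory and no go/no-go rule depends on it.

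What remains is that the choices are unstated, ordinary likelihood is at best slightly liberal and at worst clearly so, and the better method is readily available.

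**Conclusion.** The point holds as a minor improvement to section 5.4.2. At an assumed 5% level, per-predictor error is about 6-9% (joint) or 5-7% (single) at 44 patients, and about 18-26% (joint) or 6-9% (single) after a stage-1 stop. The plan's own design makes that stop 49% likely at 35% CR and 10.5% likely at 50% CR. How often no finite estimate exists at 44 patients turns on an unknown favorable share, from about half of trials at 5% to about 1% or less at equal thirds. After a stop it is about half to three quarters whatever the share.

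The results rest on null simulations with independent normal covariates. They concern the logistic models only. Extending them to the Cox models is tempting, but those were not tested. The primary CR estimate, the two-stage rule and the mortality rule are unaffected.

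**What to change.** In section 5.4.2:
1. Fit the logistic models for CR by Firth's penalised likelihood, with penalised likelihood ratio tests and penalised profile intervals.
2. State whether predictors enter jointly or singly, and the test level.
3. State that, if accrual stops at stage 1, predictors of CR are reported descriptively without tests.
4. Label the results exploratory. Firth does not remove the multiplicity of four tests.

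Keep the three cytogenetic classes unless the sponsor prefers to merge them; that is a trade-off, not a correction.

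The cost is a few sentences and standard software. Estimates shrink slightly towards no effect, and the tests are conservative at 16 patients (about 1-3%), which matters little if none are done there. A finite estimate from one or two favorable-risk patients still carries little information, so class counts should be shown beside each odds ratio.
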